### 3 SYNOPSIS

Study Title	Phase 1 Study of Treatment of Pain and Autonomic Dysreflexia by Deep Brain Stimulation in Participants with Spinal Cord Injury
Study Rationale	
Spinal cord injury (SCI) is a devastating disease, which exerts a disproportionate medical, social, and economic toll on society. Effective treatments are urgently needed for SCI, whether for immediate relief of symptoms or longer-lasting functional recovery. It (SCI) produces chronic loss of motor control, sensation and autonomic regulation below the level of the injury. Frequently disconnection is not total and some degree of below injury function remains. Unfortunately, the remaining functional connection can cause additional problems for patients (at least 20% of all SCI patients). In addition, dangerous rises in blood pressure can be produced by strong sensory input. This phenomenon is known as autonomic dysreflexia (AD). It occurs in 48% to 90% of patients with tetraplegia or high quadriplegia.
 
This study investigates the neurosurgical procedure of deep brain stimulation (DBS) in the midbrain’s periaqueductal and periventricular gray region (PAG/PVG). The use of DBS in PAG/PVG for drug-refractory non-metastatic chronic pain has been reported in the biomedical literature for at least several hundred patients, and continues to be used in many countries, including Germany and the United Kingdom. A small proportion of reported cases (about 21) of DBS applied at any brain site involved pain from spinal cord injury (SCI), and only 3 or 4 for the PAG/PVG. These reports, some of them from the 1970s, did not describe systematic studies. Extensive, modern pain testing was not done. The stimulation was not given time to work (it could require several weeks for effects to appear). The pathologies were in most cases inadequately characterized. Also, some preclinical evidence suggests PAG/PVG-DBS can also improve other SCI symptoms, such as motor deficits and autonomic dysreflexia (AD), which were never examined. The present study is designed to provide these missing details.
 
Thus, our study seeks to examine whether the safety and efficacy of prolonged DBS for SCI are sufficient to warrant its larger-scale study as therapy for pain and AD in SCI patients.

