## Conclusion

DBS in the midbrain PAG/PVG reverses ongoing pain in man. However, the data are too few to judge safety or efficacy for SCI pain. Because current drug or cognitive therapies fail to control SCI pain in a significant proportion of cases, a renewed assessment of DBS in the PAG/PVG is justified. The assessment should involve a detailed characterization of pathology, treatment and outcome. Pain alleviation could also reduce ongoing autonomic dysreflexia [41], while preclinical findings suggest that permanent partial improvements in pain, autonomic deficits and motor performance could occur after prolonged stimulation. In man, spontaneous partial recovery has been noted many months after SCI, perhaps due to patterned neural activity [42]. DBS in the PAG/PVG could accentuate this restorative activity.

Comparative advantages expected of DBS for treating SCI are as follows:

- Permanently improve symptoms, not merely relieve them.
- Every type of deficit recovers, not just, for example, limb movement or sensation
- No untoward effects of prolonged stimulation, based on by animal research
- Dose can be immediately reduced or discontinued if adverse effects appear
- Existing technology can be translated without modification to the treatment of SCI
- Trophic DBS has a strong scientific support basis and theoretical basis in repair models
- Can readily be combined in a non-interfering way with drug or cell implant therapy

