## 12.5 Description of the Measures Taken to Minimize/Avoid Bias

As this is an open label safety study without a control group, no specific measures will be taken (e.g., randomization, blinding, etc.) to minimize /avoid bias. Subjects will not be randomized, and all will receive the same pattern. The subject and the primary evaluator will not be blinded to the stimulation level. Long-term changes over the course of the treatment will be analyzed by time-series analysis of the adjusted stimulation levels. Placebo effects from surgery, as well as the safety and stability of the DBS implant, will be analyzed when the stimulator is inactivated during programming adjustment sessions by investigators.

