#### Aims:

1. To evaluate any changes in pain relief in the 2nd and 3rd year of deep brain stimulation (DBS) in the midbrain periaqueductal/periventricular gray (PAG/PVG).
2. To assess needs for changes in stimulation parameters (contact selection, voltage, frequency, pulse width) to continue optimal relief.
3. To determine changes in injury status revealed by the ASIA score.
4. To uncover later-occurring adverse effects.

Enrollment. Subjects will preferably continue without a gap at the end of the original 52 week study. However, they may be enrolled at any time during the extension to accommodate the time needed to obtain regulatory approval for the extension or subjects who wish to take a break. An additional informed consent form will be used for enrollment.

Procedures. Subjects will receive continuous DBS in the PAG/PVG from the previously implanted system. They will return every 12 weeks to the study site to optimize the stimulation parameters for pain control. The optimum may drift or may not have been determined previously from the very large range of possible settings. Subjects will leave the visits with a blinded choice of settings (2 to 4, labeled A, B, C D), which they can explore at home. Preliminary findings suggest that pain changes over several days when settings are changed, and that slow recursive testing is the best way to find the optimum. Subjects may request visits

at other times for stimulation adjustment or other study related issues. Some later subjects may have a PC+S generator device implanted, which allows recording from the stimulating leads. Subjects with this device will also undergo brief recording sessions during visits, following the protocol of the first year.

Tests and questionnaires. The study extension will use only questionnaires and study forms from the original study. It will omit autonomic system testing and quantitative sensory testing. On-site assessment will be done in clinical exam rooms and offices of the Miami Project to Cure Paralysis of the University of Miami Miller School of Medicine, including ASIA assessment. If the stimulator settings are producing consistent adequate pain relief, visits may be omitted at the subject's discretion, except for weeks 104 and 156, and assessments will be made by telephone questionnaire.

The following will be assessed every 12 weeks.

- International Spinal Cord Injury pain basic data set (ISCI)
- Neuropathic Pain Symptom Inventory (NPSI)

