**Table 2. Flow sheet of Visits/Assessments**

Study Visit Schedule for the initial 52-week study period:

week ( $\pm 7$ days) >>	<<No of tests	1	2	3, 5	4, 6	5, 6	7	8	9, 11, 13, 15, 17, 19	10, 14, 18	12, 16	20, 32	21, 23, 25, 27, 29, 31, 33, 35, 37, 39, 41, 43, 45, 47, 49, 51	22, 26, 28, 30, 34, 36, 38, 42, 44, 46, 50	24, 40, 48	52
SCREENING		x														
SURGERY, or week-5,6 screening for surgery						x	x	x								
LONG-TERM DBS in PAG/PVG (note 1)									x	x	x	x	x	x	x	x
TAPERING or STOPPING of PAIN MEDICATION(S)												x			x	
COMPREHENSIVE TESTING	4		x										x			x
ABBREVIATED TESTING	5										x				x	
TELEPHONIC INTERVIEW	40			x	x				x	x			x	x		
Sites																
Miami VA Medical Center (note 2)		x	x								x	x			x	x
Miami Project in Lois Pope Life Center (note 2)				x	x				x	x	x	x	x	x	x	x
University of Miami Hospital						x	x	x								
Study Therapy																
Targeting and lead placement	1						x									
DBS and lead connection	1							x								
DBS adjustment &-or sensing / possible 5 minute inactivation	9							x			x	x			x	x
General Assessments																
Informed Consent	3	#1	#2				#3									
Spinal Cord Injury history/Demographics	1	x														
Medical history, Brief medical examination	1	x														
Drug Abuse Screening Test (DAST)	1	x														
Folstein Mini-Mental State Examination (MMSE)	4	x											x			x
Beck Depression Inventory (BDI)	9	x									x	x			x	x
(PGIC)	44								x	x	x	x	x	x	x	x
Adverse Event assessment	52		x				x	x	x	x	x	x	x	x	x	x
Vital signs (BP, SpO2, temp)	12	x	x				x	x			x	x			x	x
Patient Diary on Medications	50	x	x	x	x				x	x	x	x	x	x	x	x
Qualitative exit interview	1															x
Neuro System Exams																
ASIA Neurological Exam	4	x											x			x
Tilt table response exam (note 3)	4		x										x			x
Patient Self-assessment of Autonomic Responses	38			x	x				x	x			x	x		
Autonomic Standards Assessment	9		x								x	x			x	x
Multidimensional Pain Inventory (MPI-SCI)	4		x										x			x
Quantitative sensory testing (QST)/Allodynia	4		x										x			x
ISCI Pain Basic Data Set / NPSI	25		x		x					x	x	x		x	x	x
Imaging																
Neuroimaging - MRI study	1						x									
Neuroimaging - CT study	1							x								
Electro-cardiogram (EKG)	1						x									
Chest x-ray	1						x									
Laboratory																
CBC, Comprehensive Metabolic Panel (including Mg + , Renal & Liver Function), PT/PTT	2		x					x								

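### The unblinded, minutes-long stimulator-off reading in Section 12.5 cannot isolate placebo effects from carry-over or expectation once stimulation has been running for weeks

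*Combined protocol and SAP*

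**What the plan says.** Section 12.5 states that the study is open label, has no control group and takes no specific measures against bias. It then names one way of addressing placebo: "Placebo effects from surgery, as well as the safety and stability of the DBS implant, will be analyzed when the stimulator is inactivated" during programming sessions. The same section says: "The subject and the primary evaluator will not be blinded to the stimulation level".

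The only duration for an inactivation is in the Table 2 row "DBS adjustment &-or sensing / possible 5 minute inactivation", listed for 9 sessions. Note 1 to Table 2 places the formal pain instruments before any stimulation adjustment, so none appears to be scheduled with the stimulator off. Section 12.3 specifies a 0–10 NRS with stimulation off, 12 to 48 hours after internalization, and repeats the procedure at week 12.

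On how fast the effect moves:
- Section 12.6.1 (extension): "Preliminary findings suggest that pain changes over several days when settings are changed".
- Synopsis, study rationale, criticising earlier reports: "The stimulation was not given time to work (it could require several weeks for effects to appear".
- Conclusion of Section 8.1, among the expected advantages: "Permanently improve symptoms, not merely relieve them".
- Section 11.1, Aim 4, looks for cumulative change over 10 months of stimulation. Aim 2 concerns the effect of acute application.

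**The concern.** With one treatment group, each participant is his or her own comparator, and Section 12.5 offers the off reading as the means of judging placebo. That works only if relief from stimulation has gone by the time the off score is taken, and if knowing the device is off does not change the score. The protocol supports neither condition. Several of its statements point to slow or lasting effects, and the reading is open.

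Two errors can follow, in opposite directions. Slow relief still present at 5 minutes looks like placebo and understates stimulation. A pain rise caused by knowing the device is off looks like lost benefit and overstates stimulation. Efficacy is part of the primary objective (Section 11.3), and the study is meant to inform whether a larger one is warranted, so a mislabelled placebo component matters even in a descriptive report.

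**Working it through.** **Session count.** The Table 2 inactivation row is marked at weeks 8, 12, 16, 20, 24, 32, 40, 48 and 52. That is 9, matching the table's own count. Eight of these (week 12 on) follow weeks of stimulation. The plan gives no numerical figure for the placebo reading, so there is nothing else to reproduce.

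**What the two readings contain.** Let P be the placebo relief and D the relief from stimulation. Let r be the share of D still present when the off score is taken, and e the rise in reported pain from knowing the device is off.
- Off-state change from baseline = P + rD − e
- On-minus-off contrast = (1 − r)D + e

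Their sum is P + D. Two observed quantities cannot determine four unknowns. The off reading equals P only if rD − e = 0; in practice that means r = 0 and e = 0.

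**Size of r at 5 minutes.** The documents give no time to offset, so the half-life h is an assumption and a range is shown. With exponential decay of all relief, r = 0.5^(5 min / h):

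| Assumed h | Exponent | r |
|---|---|---|
| 5 minutes | 5/5 = 1 | 50% |
| 1 hour | 5/60 = 0.0833 | 94.4% |
| 1 day | 5/1440 = 0.00347 | 99.8% |
| 3 days | 5/4320 = 0.00116 | 99.9% |

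**Illustration on the NRS** (assumed D = 2, P = 1, e = 0; total relief 3):
- h = 5 minutes: off change = 1 + 2 × 0.5 = 2.0; contrast = 3 − 2.0 = 1.0.
- h = 1 hour: off change = 1 + 2 × 0.944 = 2.89; contrast = 0.11.
- h = 3 days: off change = 1 + 2 × 0.9992 = 2.998; contrast = 0.002.

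The true placebo component is 1 in every row.

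**Adding expectation** (h = 3 days, assumed e = 0.5 to 1.5): off change = 2.998 − e = 2.50 to 1.50; contrast = 0.002 + e = 0.50 to 1.50. Nearly all of that contrast is expectation.

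**The early off reading.** The off-state NRS in Section 12.3 precedes chronic stimulation, so rD is close to zero there apart from the brief intraoperative test stimulation (Sections 14.3.2 and 14.3.4). It does contain any short-term analgesia from electrode insertion, which Section 8.2 describes, and recovery from surgery.

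**The case against.** The strongest reply is that the study is openly uncontrolled and descriptive, that no endpoint or stopping rule depends on the off reading, and that a fast component clearly is expected. Aim 2 tests acute application, and Section 12.3 steps the voltage contact by contact against the NRS within one session. Section 14.3.4 says effects reverse on cessation, though it gives no time. The several-days remark is preliminary, comes from the extension, and concerns changes of settings rather than switch-off. Table 2 does not tie the 5-minute inactivation to the placebo analysis.

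Much of this stands, and it rules out several stronger readings that a reader might infer:
- *That whatever the off reading shows will be labelled placebo.* Section 12.5 states no attribution rule; it says only when placebo effects will be analyzed.
- *That the off reading is the only internal check.* Section 12.3 has the pre-chronic off score, Section 12.5 also plans a time-series analysis of stimulation levels, and Section 12.7 D follows patients who stop. These are weak and unblinded, but they exist. The placebo contrast in Section 17.1 adds little, because its factor levels A to D are not defined in the text.
- *That about 99.9% of relief would be booked as placebo.* That needs all relief to decay over days, and the documents imply a mixture of fast and slow relief in unknown proportions.
- *That the extension already runs blinded off/on testing.* It says "Subjects will leave the visits with a blinded choice of settings", but describes no off or sham setting and no random order.

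What the reply does not remove is the sentence in Section 12.5. Acknowledging an open-label design does not make an open, minutes-long off score a placebo estimate.

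**Conclusion.** The point holds in a limited form. From week 12 on, the in-session off reading cannot separate placebo effects from slow carry-over or from expectation at a known switch-off. The two biases oppose each other and the net direction cannot be determined from the documents.

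On the assumption that all relief decays exponentially, 94% to 99.9% remains at 5 minutes for half-lives of 1 hour to 3 days, and 50% for a half-life of 5 minutes. Any fast component lowers these shares. Only an offset well under 5 minutes, together with no expectation effect, would make the reading clean, and no section states such an offset. The half-lives and NRS values are illustrations, not figures from the plan. The conclusion that the components are not separable does not depend on them.

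**What to change.** 1. Replace the Section 12.5 sentence. Describe the in-session off/on contrast as estimating only the immediate, rapidly reversible component of stimulation, and do not present it as measuring placebo effects from surgery.
2. Designate the off-state NRS in Section 12.3, taken 12 to 48 hours after internalization and before chronic stimulation, as the implant-without-stimulation reading. State that it is scored before the first contact is tested, and that it includes insertional analgesia, surgical recovery and any residue of intraoperative test stimulation.
3. Within the inactivation already planned in existing sessions, score the NRS in off and on segments in random order, with the subject not told the state. If masking succeeds, e is zero and the contrast equals (1 − r)D, the immediate component.

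Cost: a wording change and a few extra minutes per session, with no new visits or staff. Some subjects may guess the state from sensations, and the evaluator may still know it. The slow placebo component remains unestimated, and the report should say so.

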## 12.6 Duration of Subject Participation

- Participants will be monitored throughout a one year evaluation period for occurrence of AEs (acute, delayed, and/or cumulative), as well as for changes in clinical status, neurological status.
- Safety and efficacy assessments will be performed at week 1 and 2 post-intervention and at 4-week intervals post-intervention from study week 8 until study week 24, and at 8-week intervals thereafter until study week 48 . The last one of these assessments will take place on study week 52. The week 52 assessment will include a qualitative exit interview with audio recording. The subject and investigators will be given the opportunity for open comments and questions concerning elements of the study.
- After the initial 52-week study period subjects can choose to remain in the study for an extended period lasting approximately 104 weeks. The details of this extension period are covered next in section 12.6.1.

### 12.6.1 Extension of study

Introduction. The study will be extended for approximately 2 more years, precisely 104 weeks. The purpose is to obtain long-term follow-up information on safety and efficacy, in subjects that have opted to receive continuing brain stimulation. We label weeks in terms of original enrollment. Thus the surgery occurs in weeks 7 and 8 and the original study finishes in week 52, with the extension lasting from week 53 to week 156.

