- Beck depression inventory (BDI)
- Guy-Farrar patient global impression of change (PGIC)
- Medication usage

In addition, subjects will be asked to keep a pain diary with a morning and evening pain score rated from 0 (no pain) to 10 (worst ever pain). The pain diary will be retrieved at the visits or by telephone.

At weeks 104 and 156, we will determine the ASIA score (American Spinal Injury Association neurological examination, sensory and motor). On week 156, an open ended qualitative exit interview will be conducted with audiovisual recording, including questions on the overall experience, effects on daily life, etc.

Adverse events (AEs) will be recorded immediately after telephone contact by the subject (subject-reported AEs) and during visits to the study site (clinician-reported AEs).

• **Table 1: List of Procedures for planned study**

Screening:	
1	Urine pregnancy test
2	HIV, HBV, HCV testing
3	Laboratory tests (CBC, CMP, BSCP, prothrombin time test)
4	Medical history, Brief neurological and medical examination
5	Autonomic dysreflexia assessment
6	Spinal Cord Injury history
7	ASIA motor / sensory scores
8	Functional and pain assessments
9	Psychological Assessment (MMSE, BDI)
10	Drug abuse screening test
Baseline Procedures (at 2- weeks):	
1	Autonomic dysreflexia assessment
2	Functional and pain assessments
3	Psychological Assessment (MMSE, BDI)
4	ASIA motor / sensory scores
5	Medical history, Brief neurological and medical examination
6	Patient diary on medications
DBS Device Implantation Surgical Procedure:	
1	Initial MRI / CT scan of the spine
2	Chest X-ray; Electro-cardiogram
3	1-Targeting & Lead placement: at 7-week
3	2-DBS & Lead connection: at 8-week
ICU Monitoring/Medical Treatment:	
1	Blood Pressure Monitoring
2	Oxygenation
3	Additional physiological monitoring specific to subject (displayed on telemetry monitor)
4	Laboratory tests (CBC, CMP, BSCP, prothrombin time test)
5	Post op medications (antibiotics, DVT prophylaxis, etc.)
Follow-Up Procedures:	
1	Long-term DBS in PAG/PVG starting on week 8
2	Telephone interview: weekly, except on-site visit weeks, from week 3
3	Pain assessments: on even weeks, starting on week 10
4	Autonomic Standards Assessments: on on-site visit weeks
5	Tilt table response exam: at 20-week, 32-week, and 52-week
6	Beck Depression Inventory: on visit weeks
7	Folstein Mini-Mental State exam: at 20-week, 32-week, and 52-week

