### D. Partial Termination

If the treatment appears at any point to be clearly successful in any patient, the choice of constant stimulation at the best amplitude will be offered. Regardless of whether the stimulation is stopped permanently or left at a constant level, the patient will be followed according to the study plan for as long as they remain willing. The patient may also elect to receive no further stimulation but to stay in the full study to assess pain and other variables.

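### Years 2–3 plan no blood pressure or heart rate reading although hypotension is the named site-specific harm; secondarily, subjects with stimulation off have no scheduled contact after week 52

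*Combined protocol and SAP*

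**What the plan says.** **Extension.** Section 12.6 says that after week 52 "subjects can choose to remain in the study for an extended period lasting approximately 104 weeks" and refers to 12.6.1 for the details. Section 12.6.1 states the purpose as long-term safety and efficacy information "in subjects that have opted to receive continuing brain stimulation". Its fourth aim is "To uncover later-occurring adverse effects". On treatment it says "Subjects will receive continuous DBS in the PAG/PVG from the previously implanted system". Visits are 12-weekly to adjust the settings, and subjects go home with two to four blinded settings to explore.

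**Assessments in the extension.** The 12-weekly list is the ISCI pain data set, NPSI, BDI, PGIC and medication use. To this are added a twice-daily pain diary, the ASIA examination at weeks 104 and 156, an exit interview at week 156, and adverse events taken by telephone and at visits. On autonomic measures the text is explicit: "It will omit autonomic system testing and quantitative sensory testing". When relief is consistent and adequate, a subject may skip visits, "except for weeks 104 and 156, and assessments will be made by telephone questionnaire".

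**Stopped stimulation.** Section 12.7 D says: "Regardless of whether the stimulation is stopped permanently or left at a constant level, the patient will be followed according to the study plan". The patient's willingness sets the only limit. A patient may also take no further stimulation and stay in the full study.

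**Safety framework.** Section 15 a) separates general DBS or SCI problems from problems due to the PAG/PVG site. Hypotension is its example of the latter. Events of that second kind lead to discontinuation of treatment unless special circumstances in the patient explain them.

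**The concern.** The extension sets out to find late harm, and exposure is not constant during it, because settings are re-optimised and subjects switch among several at home. The protocol itself expects this target to act on blood pressure. Section 12.3 has cuff pressure taken before and during stimulation at first programming and again at week 12. The surgical exclusions in 13.4 rule out anyone who cannot be stimulated at analgesic levels without clinical hypertension or hypotension. Section 15 a) ties a treatment decision to such an event. Against that background, a follow-up schedule with no pressure reading leaves the most specific anticipated harm to symptoms alone.

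The second question concerns subjects who still have the hardware but no longer use it. Section 10 lists erosion, migration and delayed infection as implant risks, and these do not depend on stimulation. Section 14.4 expects few requests for removal. If the only plan for weeks 53–156 is written for subjects on stimulation, late hardware events in the others may come to light only when the subject or a treating physician reports them.

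**Working it through.** No sample-size or power formula applies. The check is a count of scheduled measurements and a comparison of sections.

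*Length of the extension (12.6.1).* 156 − 53 + 1 = 104 weeks, as stated.

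*Blood pressure and heart rate.*

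| Measure | Year 1 (Table 2) | After implantation (after week 8) | Weeks 53–156 (12.6.1) |
|---|---|---|---|
| Vital signs, including blood pressure | weeks 1, 2, 7, 8, 12, 16, 20, 24, 32, 40, 48, 52 = 12, matching the table's own count | 8 | 0 listed |
| Autonomic Standards Assessment (blood pressure, heart rate) | weeks 2, 12, 16, 20, 24, 32, 40, 48, 52 = 9, matching the table's own count | 8 | 0 listed; autonomic testing omitted |

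Table 2 is headed as covering only the initial 52 weeks, so it supplies no reading later. The week 104 and 156 visits cannot be skipped, so each subject followed to the end has at least 2 occasions on which a cuff could be used without adding a visit.

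*Device-off subjects.* What applies, and until when:

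- To week 52: 12.7 D and Table 2 keep a willing subject on the full schedule, including adverse event assessment. Appendix 1 item 5.1 requires all events since the last visit to be recorded at each required visit.
- Serious events and deaths: definition 6.15 runs to 30 days after study completion. Appendix 1 item 3.1 gives a window for adverse events generally, to 30 days after the last voltage output.
- Open events: followed until they settle (Appendix 1 items 2.2, 3.1 and 3.2).
- Afterwards: device-related serious events found post-study are still reportable (Appendix 1 item 4).
- Scheduled contact in weeks 53–156: none is written for a subject with the device off. The telephone assessment in 12.6.1 replaces a visit only for subjects whose settings give adequate relief.

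*Possible size of the second gap.* The documents do not say how many subjects will have stimulation off, so I assume 2 to 6. Table 3 gives per-patient hardware rates. Reference 2: generator migration 4% + erosion 3.2% + infection 1.6% = 8.8%. Reference 3: erosion 0.4% + infection 1.3% = 1.7%. If the whole of each rate fell in weeks 53–156, which overstates it, the expected number of events lies between 2 × 0.017 = 0.03 and 6 × 0.088 = 0.53.

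*Calls needed.* 104 / 12 = 8.67, so about 8 per subject; 2 × 8 = 16 to 6 × 8 = 48 in all.

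**The case against.** **On blood pressure.** Dropping autonomic testing is a stated choice, made after eight post-implant visits with readings. Adverse events are still collected. Appendix 1 item 5.1 adds a prompted question and presupposes a clinical examination at visits, so symptomatic hypotension should be found. The extension reuses study forms from year 1, which could include a vital-signs form. Most of this stands, and it limits the gap to changes without symptoms. But no such form or reading is named in a list that is otherwise specific, and a cuff reading is not the autonomic test battery.

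**On device-off subjects.** A reader might infer that 12.6 and 12.7 D promise these subjects follow-up to week 156 and that 12.6.1 breaks the promise. The documents do not support that. Section 12.6 defers to 12.6.1 for the details, the extension has its own consent form, and the study plan in 12.7 D can be read as the 52-week plan. Limiting a separately consented extension to those continuing therapy is a legitimate choice of scope. A reader might also infer from Appendix 1 item 3.1 that a subject who stops early drops out of safety reporting 30 days later. That does not hold either, given Table 2, item 5.1 and definition 6.15.

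Subjects also have 24-hour access to staff (10.1) and may request unscheduled visits (14.3.5). Effects of stimulation are described as reversible once it is off (14.3.4). Erosion and infection usually produce signs that the patient notices, and the expected number of events is below one under the assumptions above. What remains is that contact after week 52 is passive and that the text leaves the reach of 12.7 D open.

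**Conclusion.** The main point holds. The extension looks for late adverse effects while settings continue to change, yet plans 0 blood pressure or heart rate readings in 104 weeks, against 8 post-implant visits with both in year 1. A symptomless change in years 2–3 would not be measured by plan. This rests on reading the listed extension assessments as complete.

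The secondary point holds in a narrow form: after week 52 no active contact is scheduled for subjects who keep the hardware with stimulation off, and it is unclear whether 12.7 D was meant to cover them. It does not amount to a contradiction between sections or to loss of safety reporting. Its size depends on a number the documents do not give, which may be zero.

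The 52-week safety and efficacy analyses are not affected. Severity is minor; the case for acting is that the changes are cheap.

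**What to change.** 1. In 12.6.1, add cuff blood pressure and heart rate at every extension visit that is held, and at least at weeks 104 and 156. The cost is minutes per visit and one edit to the text. A single reading will not catch brief episodes, but it will show a sustained change.
2. State whether 12.7 D reaches into the extension. Offer each consenting subject with hardware in place and stimulation off a 12-weekly telephone call with an adverse event and device question. This is a small new contact of about 8 calls per subject (16 to 48 in all for an assumed 2 to 6 subjects), plus an edit to the extension consent form. Some will decline, and nothing can be collected once consent is withdrawn, so coverage will not be complete.
3. When late events are reported, give the number of subjects followed and do not count implanted subjects who were not followed as event-free. This costs a sentence in the report.
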